6.3. Other Endpoints

6.3.1. PK Endpoints

Steady-state trough concentrations (C_{trough}) of bosutinib will be determined. A total of 1 PK samples per subject will be drawn. All patients will provide a pre-dose blood sample following at least 2 weeks of uninterrupted dosing with bosutinib at the same dose level. This sample will be collected at their first scheduled visit following all appropriate approvals and implementation of protocol amendment # 1. Biological specimen samples for pharmacokinetic analysis must be identified with labels provided by the sponsor.

Concentrations of bosutinib will be determined in plasma using a Pfizer -approved and validated liquid chromatography/tandem mass spectrometry (LC/MS/MS) assay.

The objective of the pharmacokinetic analysis is to compare the C_{trough} of bosutinib in this study to C_{trough} of previous studies. Definitions of and analyses for PK parameters will be outlined in a formal PK analysis plan and will not be included in this SAP.

6.3.2. PD Endpoints

There are no PD data being collected in this study.

6.3.3. Outcomes Research Endpoints

There are no outcomes research data being collected in this study.

6.4. Covariates

Subgroup analyses by gender, age (<65, ≥65), and race (Asian, Black, Other, White) will be explored as deemed appropriate. Additional supportive analyses may be explored if deemed appropriate.

The randomization in B1871008 was stratified by region and Sokal score; however, since only bosutinib patients from B1871008 are eligible for B1871040, none of the CP1L analyses will be stratified.

7. HANDLING OF MISSING VALUES

In general, no imputation such as last observation carried forward (LOCF) will be used. For the time-to-event endpoints, such as DOR, time to transformation, PFS, and OS, the primary missing data handling method will be censoring as described in [Section 6.1](#).

In compliance with Pfizer standards for handling partial dates, if the month and year are present but day is missing, start date is set to 1st of month, and stop date is set to last day of month. If year is present but day and month are missing, start date is set to January 1st, and stop date is set to December 31st.

Handling of missing/incomplete patient cytogenetic data from parent study B1871006 was done by the following procedure: for B1871006 baseline visits, only bone marrow information is used. If <20 metaphases at baseline, patients with ≥8 Ph+ will be assigned a minor response and those with 1 to 7 Ph+ will be assigned a partial cytogenetic response (PCyR). For post-baseline visits in B1871006 and B1871040, bone marrow information with 20 to 100 metaphases will be used over FISH information with at least 200 nuclei at a specific visit. No conventional bone marrow cytogenetic assessment will be derived when >100 cells are reported as analyzed for Philadelphia chromosome as this will be considered an error in data entry. If on-treatment molecular monitoring is performed for visits in B1871040 in lieu of conventional cytogenetics or FISH, CCyR may be imputed on a specific date if an MMR or better is achieved and denoted on the CRF on that date. The results of conventional cytogenetic testing, banding with ≥20 metaphases, will be used in preference to molecular testing, provided they are available and performed on the same date however molecular results will be used over FISH with ≥200 nuclei if results are discrepant. Handling of missing/mismatched patient hematologic efficacy data for from parent study B1871006 was done using the following procedure: for each patient, the observations were sorted by visit and the relative day to first dose from B1871006.

First, for each observation, peripheral blood and/or bone marrow differentials should add up to 100%. Some sites may not record 0% to reflect uncounted cell types as instructed. Instead, the corresponding field may appear as missing or “ND” even though data collection procedures have been vigorously followed. Also, the differentials may not exactly add up to 100%. To correct this problem, each domain of the differentials was summed together.

If the total was between 98.5% and 101%, the missing values were assigned 0%. Otherwise, the observation was left as is and the record was also to be reported as a data issue.

Second, for the set of variables collected to derive peripheral blood or bone marrow differentials at each post-baseline visit through week 12 on B1871006, if a given set were still incomplete, a non-missing set of lab variables obtained ± 3 days from the scheduled visit was utilized to complete the derivation. For visits after week 12 (relative to first B1871006 dose) from B1871006 and B1871040, a non-missing set of lab variables obtained ± 7 days of the visit will be utilized to complete that post-baseline assessment. For B1871006, the last non-missing peripheral blood or bone marrow differentials collected at week 1 day 1 or up to 28 days prior to week 1 day 1 was used for baseline assessment. For example, if the bone marrow blast count was missing, the entire non-missing bone marrow assessment, not just the blast field, from another observation was used. Some data handling rules for data combination are specified below.

- Data combination is needed only when the full dataset is not available on a single day at a given visit. The full dataset includes peripheral blood differential for chronic phase, and both bone marrow and peripheral blood differentials for advanced phase. The extramedullary assessment when absent should not preclude the derivation, and when present should be taken into account per response criteria rules.
- During the post-baseline data combination, for visits up to and including week 12 from B1871006, the ± 3 window will be applied to days 1 and 7 separately; for visits after week 12 (relative to first B1871006 dose) from B1871006 and B1871040, the ± 7 window will be based on day 7 only. The latest date will be used as the date of visit and the more conservative value will be taken if there is more than one measurement for a variable. For platelet counts, in case of multiple values, the lowest value will be taken. If any value falls above or below normal range, the out-of range value will be taken.

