9.1. Sample Size Determination

This study does not include any formal sample size determination. All bosutinib patients from the two parent studies B1871006 and B871008 who are still on-treatment at the initiation of this study, or known to be alive as of their last LTFU visit, or who have completed the parent study will be offered enrollment in this extension study.

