4. HYPOTHESES AND DECISION RULES

4.1. Statistical Hypotheses

There are no statistical hypotheses in this study.

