6.2. Safety Endpoints

Treatment-emergent adverse events (TEAE) were defined as any event increasing in severity from baseline or any new event starting during bosutinib therapy or within 30 days of the last dose of study drug.

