6.2.7. Adverse Events of Special Interest

Adverse events including ALT, AST, thrombocytopenia (including MedDRA preferred term [PT] Platelet Count Decreased), neutropenia (including PT Neutrophil Count Decreased), anemia (including PT Hemoglobin Decreased), diarrhea, nausea, vomiting, cardiac toxicity (definition to be determined before DBL), vascular toxicity (definition to be determined before DBL), and renal toxicity (definition to be determined before DBL) will be summarized. Additional AEs or AE clusters may be summarized if deemed appropriate. AE characteristics to be summarized include maximum toxicity, time to first event, duration of any grade event, cumulative duration of grade 3/4 events, and successful rechallenge (those patients who were re-dosed and did not discontinue bosutinib due to this AE after having a dose delay).

The diarrhea characteristics will also be summarized separately for data from B1871008 and B1871006 compared to B1871040 in order to assess the impact of changing to the clinical formulation of bosutinib from the parent studies to the commercial formation in this study. For ongoing events at the time of the switch to commercial formulation, the stop date for the event attributed to the clinical formulation will be set to date of the start of commercial formulation minus one and the start date for the event attributed to the commercial formulation will be set to the start date of commercial formulation.

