8.2.2.8. Adverse Events of Special Interest

The number and percentage of maximum treatment-emergent CTCAE grade events and successful rechallenge for ALT, AST, thrombocytopenia (including MedDRA PT Platelet Count Decreased), neutropenia (including PT Neutrophil Count Decreased), anemia (including PT Hemoglobin Decreased), diarrhea, nausea, and vomiting will be summarized. Descriptive statistics for time to first event, duration of any grade event, and cumulative duration of grade 3/4 events will be calculated for each of these parameters.

The number and percentage of maximum treatment-emergent CTCAE grade events over time for diarrhea will be summarized. Only patients receiving treatment within a given time period will be included in the denominator for this time period. The incidence relative to the first dose of both the parent studies and the first dose of B1871040 will be calculated separately. Furthermore, the incidence relative to the last dose of bosutinib from the parent studies will also be calculated in order to see the percentage of patients experiencing diarrhea during the last 6 months prior to enrolling in B1871040. Time to first event in B1871040, defined as any new event in B1871040 or any increase in severity for ongoing events from B1871006 or B1871008, and duration of B1871040 events will also be summarized.

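### Partial AE start dates have no floor at first dose, so events that began after dosing in the first-dose month or year are dated pre-treatment and lost as TEAEs; the formulation comparison has a smaller, related error.

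*SAP*

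**What the plan says.** SAP section 7 gives a general rule for partial dates, described as following the sponsor's standards. For a missing day, "if the month and year are present but day is missing, start date is set to 1st of month"; the stop date goes to the last day of the month. For year-only dates, "If year is present but day and month are missing, start date is set to January 1st, and stop date is set to December 31st". The rule does not name AEs and gives no exception around first dose or the formulation switch.

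Three AE rules depend on the start date:

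- SAP section 6.2 defines a TEAE as "any event increasing in severity from baseline or any new event starting during bosutinib therapy or within 30 days of the last dose".
- SAP section 6.2.7 splits diarrhea events at the switch. The rule opens "For ongoing events at the time of the switch to commercial formulation, the stop date for the event attributed to the clinical formulation"; the clinical part ends the day before commercial dosing starts, and the commercial part begins on that first day.
- SAP section 8.2.2.8 summarizes time to first event in B1871040, "defined as any new event in B1871040 or any increase in severity for ongoing events from B1871006 or B1871008". It also reports diarrhea in the last six months before enrolment in the extension.

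None of the three says how a partial start date is handled.

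**The concern.** Setting a start date to the earliest possible day is harmless when that whole month or year lies after first dose. It is not harmless in the month or year that contains first dose. There the earliest day nearly always precedes treatment, and an event that began on bosutinib becomes a pre-existing condition. Unless its severity then increased from baseline, it meets neither limb of the TEAE definition.

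This affects early-onset toxicity most. Protocol section 1.2.2 reports that diarrhea in the first-line study fell mostly in the first one to two months of therapy, so the exposed period is where diarrhea clusters after starting bosutinib.

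The same mechanism operates at the switch to the commercial product, and the diarrhea comparison across that switch is an EMA post-approval requirement. A false pre-switch event raises the clinical-formulation reference, and loss of new-event status removes an event from the B1871040 time-to-first-event summary. Both errors favour the commercial product.

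**Working it through.** The plan has no figure to reproduce: "There are no statistical hypotheses in this study", and "This study does not include any formal sample size determination". The check is therefore on the calendar. Call first dose, or the switch, the anchor.

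**1. Events in the anchor month or year.** Take a month of 30.4 days (the SAP's divisor in section 6.2.1) and a year of 365.25 days. An event starting on or after the anchor in the same month is back-dated before it unless the anchor is the 1st.

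- Very early onset: every anchor day has about equal weight, so the share moved is 1 - 1/30.4 = 96.7%. Year-only: 1 - 1/365.25 = 99.7%.
- Onset spread evenly over a long period: an anchor on the 1st leaves more days in the month and so carries more weight, and the share moved is 1 - 2/(30.4 + 1) = 93.6%. Year-only: 1 - 2/(365.25 + 1) = 99.5%.

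A simulation of 400,000 events, with anchors uniform over four calendar years, gave 92.4-96.4% for day-missing events and 99.5-99.7% for year-only events. The lowest value comes from the scenario with the fewest anchor-month events (onset uniform over 120 months).

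**2. All partial-date events with onset after the anchor.** For day-missing events with uniform onset over W days, the average exposed time is (30.4 - 1)/2 = 14.7 days, so the share moved is about 14.7/W. Over 3 months this is 14.7/91.2 = 16.1%; over 60 months it is 14.7/1824 = 0.8%. Simulated results:

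| Assumed onset after anchor | Day missing: moved | Year only: moved |
|---|---|---|
| Uniform, 3 months (diarrhea card period) | 16.2% | 87.5% |
| Uniform, 11 months | 4.4% | 54.1% |
| Uniform, 16.6 months | 2.9% | 36.2% |
| Uniform, 60 months | 0.8% | 10.0% |
| Exponential, mean 1 month | 35.8% | 91.5% |
| Exponential, mean 7 days | 75.6% | 97.9% |
| Exponential, mean 3 days | 88.4% | 99.1% |

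The 11 and 16.6 months are the median treatment durations of the two larger studies in Protocol section 1.2.2. All onset distributions are assumptions.

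**3. Size of the loss.** The documents do not give the share of AEs with a partial start date. If 1-5% of early-onset AE records lacked the day, the share of records lost would be 0.485 × 1-5% = 0.5-2.4% with onset uniform over the first month (48.5% moved), or 0.884 × 1-5% = 0.9-4.4% with a mean onset of 3 days. The 1-5% is illustrative only.

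**4. The switch.** Suppose the switch is on 10 September and a new event runs from 18 to 25 September, with the start day missing.

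- Section 7 dates the start 1 September.
- Section 6.2.7 treats the event as ongoing at the switch: clinical 1-9 September, commercial 10-25 September.
- The commercial count keeps the event. The clinical count, including the last-six-months figure, gains one that never occurred.
- Under section 8.2.2.8 it is no longer new, so it drops out of time to first event in B1871040 unless severity increased.

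A truly post-switch event cannot stop before the switch, and a partial stop date goes to month-end or December 31. The split therefore always keeps it under the commercial product.

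**5. With a floor at the anchor,** no event with true onset on or after the anchor was placed before it in any scenario.

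**The case against.** The strongest reply has five parts.

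- **The sponsor's standard may already contain a floor.** This is possible, but the SAP states an operative rule without one, and a programmer following the text would back-date.
- **Most partial dates are unaffected.** This stands. A reader might infer that nearly all partial-date AEs are misplaced, but that holds only within the anchor month or year. With onset spread over 3 to 60 months, about 1-16% of day-missing events move.
- **Diarrhea is not moved off the commercial product.** This also stands. A reader might infer such a shift, but the section 6.2.7 split prevents it. What remains is a false extra clinical event and lost new-event status.
- **The switch is the best-documented period.** Protocol section 7.2.2 and Appendix 2 provide a diarrhea card with a full date field for the first three months, reviewed by the investigator. Missing days should be least common there. The early clustering of diarrhea refers to starting bosutinib, not to long-term users changing formulation, so it supports only the first-dose part of the point.
- **The summaries are descriptive and count patients.** A lost record changes a percentage only if the patient has no other qualifying event of that term. This limits the size of the error but not its direction.

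SAP section 6.2.3 restricts laboratory event timing to complete dates. Section 6.2.7 does not repeat this for AEs, and it would not settle TEAE status or incidence in any case.

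**Conclusion.** The point holds at first dose. As written, section 7 dates about 92-96% of day-missing events in the first-dose month, and 99.5-99.7% of year-only events in the first-dose year, before treatment when they truly began after it. Those events are lost as TEAEs unless severity increased from baseline. At that boundary the error can only reduce TEAE counts. Its absolute size is unknown, because it depends on how many AE start dates are partial and how early those events occur.

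At the switch the error is narrower: an extra clinical-formulation event and a lost new event in B1871040, with the commercial count intact. The conclusion assumes that section 7 applies to AE dates and that no unstated floor exists in the sponsor's standard. Because a stated rule gives a wrong answer for a core safety output and is cheap to correct, it should be changed even though the study tests nothing.

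**What to change.** Add to SAP section 7: if the known month (day missing) or year (day and month missing) of a partial AE start date equals that of first bosutinib dose, and the stop date is not before first dose, set the start date to the first dose date; otherwise keep the existing rule.

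For the formulation comparison, do not floor every compatible date at the switch. A year-only event in the switch year that truly began on clinical product would be pushed onto the commercial product, and a stop date imputed to December 31 would always pass the check. Instead:

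- treat a partial-date event first recorded in B1871040, and not ongoing in the parent study data, as new, with a start no earlier than the first commercial dose;
- leave events recorded in the parent study under the clinical formulation, subject to the existing split.

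Also state in section 6.2.7 whether AE timing and duration use complete dates only.

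The cost is a few sentences and a small programming change. Some events that truly began before first dose, in the same month or year, will count as treatment-emergent, chiefly those whose stop date is also partial. That is conservative for safety.

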1. AMENDMENTS FROM PREVIOUS VERSION(S)

The SAP version 3.0 amended the original SAP v2.0 dated November 16, 2016. The main changes are COVID-19 related and additional exploratory analyses which included:

- Impact on analyses from COVID-19.
- Analysis of molecular data.

The SAP version 2.0 amended the original SAP v1.0 dated April 24, 2013. The main changes to align with protocol amendment #1 included:

- Add pharmacokinetic (PK) endpoint.
- Include imputation of cytogenetic response from molecular monitoring data if cytogenetics is not performed per standard of care.
- Update appendices for cytogenetic and hematologic response criteria.

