Duration of response (DOR) is defined as the time from first response to confirmed loss, progression of disease, or on-treatment death due to any cause ([date of loss – date of first response]/7). Response is unconfirmed for cytogenetic and molecular and confirmed for hematologic with 2 consecutive responses at least 28 days apart. Confirmed loss is defined as 2 consecutive non-responses at least 28 days apart for MCyR and 14 days apart for hematologic, 1 non-response confirmed by progression of disease or death, or no loss of response and progression of disease or death. For CCyR, confirmed loss is defined as 2 consecutive assessments with >0 Ph⁺ metaphases or $\geq 1\%$ positive cells from fluorescence in situ hybridization (FISH) at least 28 days apart or progression or death. For MMR, confirmed loss is defined as 2 consecutive assessments at least 28 days apart with a <3 -log ($>0.1\%$ from B1871006 or MR² or worse denoted on the B187040 case report form [CRF]) reduction in transcripts from standardized baseline one of which corresponds to a ≤ 2 -log reduction ($\geq 1\%$ from B1871006 or MR¹ or worse denoted on the B1871040 CRF) or progression or death. For MR⁴, confirmed loss is defined as 2 consecutive assessments at least 28 days apart with a <4 -log ($>0.01\%$ from B1871006 or MR³ or worse denoted on the B187040 CRF) reduction in transcripts from standardized baseline one of which corresponds to a ≤ 3 -log reduction ($\geq 0.1\%$ from B1871006 or MR² or worse denoted on the B1871040 CRF) or progression or death. Patients without confirmed loss are censored at the last valid assessment where response could be assessed. Cytogenetic and hematologic responses are defined in [Appendix 2](#) and [Appendix 1](#). MCyR is defined as a CCyR or partial cytogenetic response (PCyR). OHR is defined as CHR or return to chronic phase (RCP). To be considered a responder, the patient must have an improvement from baseline or maintenance of baseline response for ≥ 5 weeks for hematologic response or ≥ 4 weeks for cytogenetic response. Patients with a non-valid cytogenetic assessment (<20 metaphases) or missing baseline assessment must demonstrate the best response, CCyR or CHR, to be considered a responder for the respective endpoint.

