Molecular response in B1871006 was based on the difference between the subject's change in Bcr-Abl/Abl ratio and a laboratory reference baseline. The Quest (vendor) laboratory reference Bcr-Abl/Abl ratio of 4.1325 derived from a pool of 120 previously untreated CML subjects was used as the standardized (or reference) baseline. Molecular response was not analyzed for subjects in China, India, the Russian Federation, and South Africa due to logistical constraints in transporting samples to the central laboratory.

To be considered a responder for MMR in B1871006, a subject must have had at least a 3-log reduction from the Quest standardized baseline, a detectable Bcr-Abl transcript at baseline or any time post-baseline, and must have maintained or attained a CCyR. Additionally, as a conservative approach given the known variability with standard MMR analyses, a subject who had a non-CCyR on the same day as the MMR assessment was not considered to have a MMR at that time point. MR⁴ was defined similar to MMR except at least a 4-log reduction was required. In B1871040, responders had MMR/MR⁴ or better denoted on the CRF as assessed by a local laboratory. On-treatment response is independent of a patient's baseline molecular response.

PFS is defined as the time from first dose to progression as assessed by the investigator and noted as the reason for permanent treatment discontinuation on the CRF or on-treatment death due to any cause ($[\text{date of progression/death} - \text{first dose date}]/30.4$), whichever occurs first. Patients without events are censored at the last cytogenetic, hematologic, or laboratory assessment where progression could be assessed. Progression for B1871006 patients is defined as:

- *Evolution from chronic phase (or from return to chronic phase for advanced subjects) to accelerated phase or blast crisis (on two consecutive assessments at least a week apart).*
- *Evolution from accelerated phase to blast crisis (on two consecutive assessments at least a week apart).*
- *One of the following conditions occurring after dose escalation or presence of adverse events prohibiting dose escalation:*
 - *For 2nd or later line subjects, loss of major cytogenetic response (need at least 30% increase).*
 - *For all lines of treatment, loss of complete hematologic response confirmed by 2 assessments at least 2 weeks apart.*

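### PCR at MMR can stand as a CCyR in B1871040, but no PCR result can record loss of CCyR or MCyR, so a loss seen only on PCR is censored and response duration leans long

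*SAP*

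**What the plan says.** Duration of MCyR/CCyR for B1871006 patients is a listed efficacy endpoint (SAP 6.1), analysed by Kaplan-Meier among responders (SAP 8.2.1).

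- **Gaining or keeping CCyR.** Protocol 7.1.1 allows PCR in place of cytogenetics once a molecular response is reached. Protocol 6.3 accepts either test at end of treatment. For B1871040 visits with PCR only, SAP 7 states that "CCyR may be imputed on a specific date if an MMR or better is achieved and denoted on the CRF on that date". SAP 1 dates this rule to version 2.0, written to follow protocol Amendment 1: "Include imputation of cytogenetic response from molecular monitoring data if cytogenetics is not performed per standard of care".
- **Discrepant results.** Banding with at least 20 metaphases on the same date outranks PCR. For FISH, "molecular results will be used over FISH with ≥200 nuclei if results are discrepant".
- **Losing CCyR.** SAP 6.1 requires two consecutive assessments showing Ph+ metaphases, or at least 1% "positive cells from fluorescence in situ hybridization (FISH) at least 28 days apart or progression or death". No PCR level appears. MCyR loss needs two non-responses, and SAP Appendix 2 gives PCR no cytogenetic category.
- **Losing MMR.** Here PCR levels are used: "For MMR, confirmed loss is defined as 2 consecutive assessments at least 28 days apart", both worse than MMR and one of them MR1 or worse on the B1871040 CRF.
- **Otherwise.** "Patients without confirmed loss are censored at the last valid assessment where response could be assessed".

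**The concern.** PCR can add or maintain a CCyR but cannot by itself end one. A result worse than MMR has no cytogenetic meaning in the SAP, so it is neither a response nor a loss. A PCR-only patient who relapses drops out of the risk set at about the last MMR, because of the relapse. Kaplan-Meier assumes that censored patients carry the same future risk as those who remain, and here that fails in a known direction.

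Progression is only a partial safety net. For second or later line patients, the SAP 6.1 progression list includes loss of major cytogenetic response, not of CCyR. Even that counts only after dose escalation or when adverse events prohibit it.

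Assessing the duration of clinical benefit is a stated objective (Protocol 2.1), so a listed endpoint is affected. Nothing is tested, so what is at stake is the accuracy of a descriptive curve. MCyR is affected less, because its loss requires more than 35% Ph+ cells.

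**Working it through.** The documents give no figure to reproduce: no sample size, loss rate or share of patients on PCR. The check applies the rules to one constructed patient and then sizes the effect on stated assumptions.

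**One patient, PCR only.** BCR-ABL is 0.05, 0.08, 5, 12 and 15% IS on days 0, 182, 364, 546 and 728.
- Under the SAP, days 0 and 182 are imputed CCyR and later days have no category. There is no event, and the patient is censored at day 182.
- If two results of MR1 or worse at least 28 days apart counted as loss, the loss would be dated at day 364.

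**Time under the rule.** SAP 7 sets no start date. Amendment 1 is dated 10 August 2016. SAP 8.2.1 says that all but one enrolled patient reached 10 years before 11 March 2020. The interval is 1,309 days, and 1,309/365.25 = 3.58, about 3.6 years.

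**Assumptions (none from the documents).**
- Response comes 0.5 years after first dose, leaving 9.5 years of possible duration. Visits are every 24 weeks (0.46 years).
- Progression or death is 1% per year and always recorded.
- Loss of CCyR is λ = 2% or 5% per year in patients who go to PCR only, and 5% in the others.
- The PCR-only share is 25% or 50%.
- s is the share of PCR-only losses later captured by marrow or FISH.

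**True loss at 9 years.** Losses are dated at visits, and the last visit before 9 years is 19 × 0.46 = 8.74. With a 50% share and λ = 2%:

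1 − ½[exp(−0.02×8.74 − 0.01×9) + exp(−0.05×8.74 − 0.01×9)] = 1 − ½(0.767 + 0.590) = 32.1%.

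**Understatement under the SAP rule.** It is approximately S × π × (1 − s) × λ × y.
- S is the true proportion still in response at 9 years.
- π is the PCR-only fraction of those at risk in mid-window.
- y is the affected time. The rule starts at 9.5 − 3.6 = 5.9 years, and visits run from 13 × 0.46 = 5.98 to 8.74, so y = 2.76.

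| PCR-only share | λ | s | S | π | Understatement |
|---|---|---|---|---|---|
| 50% | 2% | 0.5 | 0.679 | 0.555 | 0.679×0.555×0.5×0.02×2.76 = 1.0 point |
| 25% | 2% | 0.8 | 0.635 | 0.294 | 0.635×0.294×0.2×0.02×2.76 = 0.2 point |
| 50% | 5% | 0.5 | 0.590 | 0.500 | 0.590×0.500×0.5×0.05×2.76 = 2.0 points |
| any | any | 1 | – | – | 0 |

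Simulation of the same model agrees: 0.2 to 2.0 points over the grid with s = 0.5–0.8. The first row gives 32.0% true loss against 31.0% under the SAP rule. If no PCR-only loss were ever captured (s = 0), the largest gap would be about 4 points.

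**Marrow/FISH only, no imputation.** On the first-row assumptions, simulated 9-year loss is 40.2%. That is 40.2 − 32.0 = 8.2 points too high, against 1.0 point too low for the SAP version. PCR-only patients are then censored at the switch unless an event is recorded, so follow-up after the switch is selected for events.

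**The case against.** The strongest reply is that the effect is small and largely visible already.

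- **Losses have other ways to be recorded.** A 1-log transcript rise after MMR prompts contact with the sponsor (Protocol 5.2.1). Marrow cytogenetics may be done when FISH suggests loss or at end of therapy (Protocol 7.1.1). Progression and on-treatment death end a response. All of this favours a high s, and at s = 1 there is no bias.
- **Molecular relapse is reported elsewhere.** Duration of MMR and MR4 has its own PCR loss rule, and efficacy data are listed. There are no hypotheses or decision rules.
- **Imputing CCyR from MMR is not shown to be wrong.** Dropping it can do more harm than keeping it, as the 40.2% shows.

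These points stand and limit the size. They do not remove the asymmetry. PCR-only follow-up is foreseen by the protocol, the CRF categories needed are already used for MMR loss, and nothing in the plan makes s equal to 1.

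A reader might infer more than the documents support:

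- **That the rule covers about 7.0 years**, counted from the original protocol (25 February 2013), giving up to 4.6 points. PCR in lieu of cytogenetics and its imputation are tied to Amendment 1, so 3.6 years is the better-supported figure, though still an inference.
- **That PCR over FISH reverses a parent-study convention**, because in B1871006 "a subject who had a non-CCyR on the same day as the MMR assessment was not considered to have a MMR". That sentence decides when an MMR counts, not when a CCyR does. The SAP 7 rule that "the more conservative value will be taken if there is more than one measurement for a variable" concerns hematologic data. Which test should prevail is debatable. The defect is that the SAP does not state the direction of the rule.
- **That any PCR above MMR is a lost CCyR.** Protocol Appendix 1 puts MR2 at up to 1%, so such a result does not itself show loss.

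**Conclusion.** The concern holds. The SAP lets PCR support a CCyR and gives it no role in ending a CCyR or MCyR, so losses seen only on PCR are censored near the time they occur. The direction is towards longer CCyR duration and, to a lesser extent, longer MCyR duration. Only B1871006 responders with PCR results in B1871040 are affected.

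The size cannot be derived from the documents. On the assumed rates it is roughly 0.2 to 2 percentage points of 9-year loss when 50–80% of PCR-only losses are captured by other means, and zero when all are. This rests on about 3.6 years under the rule, a PCR-only share of 25–50%, and loss of 2–5% per year in that group.

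It would be tempting to treat the SAP analysis and a marrow/FISH-only analysis as lower and upper limits for the truth. That is not safe. With a higher loss rate in PCR-only patients (5% against 2% per year), no later capture and 7 years under the rule, true loss is 32.1%, while the two analyses give 22.1% and 30.6%. This case is less plausible clinically, but it shows that the bracket is not general.

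The point deserves correction before the analysis is final, but it does not undermine the study.

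**What to change.** 1. Add a sensitivity analysis of CCyR duration, labelled as a new definition. Two PCR results of MR1 or worse on the B1871040 CRF at least 28 days apart, or one followed by progression or death, count as loss of CCyR. PCR between MMR and MR1 is treated as not evaluable for CCyR.
2. Report the share of CCyR follow-up that rests on imputed values. As a secondary check, report duration from marrow and FISH only. State that it may lie further from the truth than the SAP version and that the two need not bracket it.
3. In SAP 7, make the imputation mandatory by replacing the permissive 'may' with 'will'. State which way the PCR-over-FISH rule works and what category a PCR result worse than MMR receives. FISH need not be given precedence.

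The cost is SAP wording, a small derivation on CRF categories already used for MMR loss, and one or two extra tables. Reported durations may be slightly shorter in the sensitivity analysis.
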